2.4 Patient disposition, demographics and other baseline characteristics

2.4.1 Patient disposition

The ENR will be used to prepare a summary and listing of patient disposition.

The number and percentage of patients who completed and discontinued from the study and treatment will be summarized with reasons for premature discontinuation for the FAS. In addition, the number of screen failures with reasons will be presented for all screened patients. The patient identification number and whether patients completed or discontinued from the study will be listed, with date of last dose and primary reason for premature discontinuation.

A separate summary of disposition and listing for rescreened patients will be presented for ENR.

Study treatment will be discontinued under the following circumstances:

- Adverse event which could lead to study treatment discontinuation
- Death
- Lost to follow-up
- Physician decision
- Pregnancy
- Progressive disease
- Protocol deviation
- Study terminated by sponsor
- Technical problem
- Patient decision
- New therapy for study indication
- Lack of efficacy
- Use of prohibited treatment
- Any situation in which study participation might result in a safety risk to the patient

2.4.2 Protocol deviation

The number and percentage of patients with protocol deviations will be tabulated by category and deviation for the FAS. Patients with protocol deviations will be listed with date and study day of occurrence, deviation and severity codes for the ENR.

The number of patients included in each analysis set will be tabulated for all screened patients. Reasons for exclusion from analysis sets will be tabulated for the ENR. Patient exclusion from analysis sets will be listed for all patients with reasons for exclusion (i.e., both protocol and non-protocol deviations).

2.4.3 Demographic characteristics

Demographic and Baseline characteristics will be listed and summarized descriptively overall patients on the FAS and the SAF.

The following demographic and vital signs variables collected in the eCRF at Baseline will be summarized:

1. Sex (Male, Female)
2. Age (in years)
3. Age category (< 50, 50 - 65, 65 - 75, 75 - 85, \geq 85)
4. Study eye (Left [OS], Right [OD])
5. Vital signs (sitting systolic/diastolic blood pressure [mmHg], sitting pulse rate [bpm])

2.4.4 Baseline characteristics

The following Baseline characteristics collected in the eCRF at Baseline will be summarized for study eye and fellow eye (wherever applicable):

- Study eye status at nAMD diagnosis (date of diagnosis, BCVA at diagnosis, CSFT at diagnosis)
- Time since nAMD diagnosis
- Time since nAMD diagnosis (< 2.5 - 5, 5- 8, 8-11, 11-18).
- Unilateral versus bilateral nAMD
- BCVA
- BCVA (\leq 55, 56 - 70, \geq 71)
- BCVA categories (Count fingers, Hand motion, Light perception, No light perception) in case BCVA score is 0

- SD-OCT (analyzed by Duke [CRC])
 1. Lesion type (only at Baseline) (type 1, type 2, type 3)
 2. CSFT (μ m)
 3. Baseline CSFT (< 300, \geq 300 - 450, \geq 450 - < 650, \geq 650 [μ m])
- Presence of fluid (Yes/No)
 1. Intraretinal fluid
 2. Subretinal fluid
 3. Sub-RPE fluid
- Volume (mm^3) and height (μm) of each fluid (in case of presence)
 1. Intraretinal fluid

- 2. Subretinal fluid
- 3. Sub-RPE fluid
- In case of sub-RPE/PED: nature: serious PED/fibrovascular PED / mixed PED
1. CNV lesion area (at the biggest surface) (mm²)
- Ophthalmic abnormalities (Yes, No)
- Disease activity assessment (Present)
- History of primary diagnosis:
 1. Disease (Neovascular Age-Related Macular Degeneration)
 2. Age of diagnosis
 3. Eye (OD, OS)
 4. Ongoing (Yes, No)
- History or evidence of the following in the study eye within the 90-day period prior to Screening/Baseline:
 1. Intraocular or refractive surgery
 2. Previous panretinal and peripheral laser photocoagulation
 3. Previous macular surgery or other intraocular surgical intervention
- Concomitant medication at Baseline
- Medical history
- Co morbidities
- Current medical condition

2.4.5 Relevant medical history/ current medical condition

Medical history/current medical conditions (general and ocular) will be coded using the Medical Dictionary for Regulatory Activities (MedDRA) terminology. History/conditions will

be summarized for the FAS by primary system organ class (SOC), preferred term (PT) by eye (study eye, fellow eye and any eye). Verbatim recorded history/conditions will be listed together with the coded terms, date of diagnosis/surgery and whether the problem was ongoing at start of the study. The ongoing medical history will be considered as co morbidities. The comorbidities will be summarized and listed separately for eye (study eye, fellow eye and any eye).

2.5 Treatments (study treatment, rescue medication, concomitant therapies, compliance)

2.5.1 Study treatment exposure

Extent of exposure to study treatment is calculated as the number of IVT injections received.

The following summaries will be presented:

1. Summary statistics of number of injection (n, q1, median, q3, min and max) will be provided.
2. Number of injections (n, q1, median, q3, min and max) before or at Week 8 and greater than Week 8.
3. Number of patients with injection category (1 injection, 2 injections up to the maximum number of injections) from Baseline to the end of the treatment period (Week 44/46) will be presented.
4. Treatment exposure by visit: The number and percentage of patients who received injections, missed a treatment and missed visits will be presented by visit.
5. The number of time the injection interval shorting and the number of time the injections interval increasing.
6. Summary statistics (n, mean, std, q1, median, q3, min and max) for overall duration will be provided.

The number and percentage of patients with changes in brolucizumab 6 mg treatment patterns over time (i.e. treatment interval adjustments, interruptions or permanent discontinuations) along with reasons, will be summarized. Discontinuations and primary reasons for treatment and/or study discontinuation will also be described.

Exposure data will be summarized on the SAF and the FAS. The exposure data will be listed on the FAS.

2.5.2 Prior, concomitant and post therapies

Each medication has the start and end dates recorded on the eCRF. Prior medications/procedures are defined as those medications which were taken and stopped prior to first dose of study treatment. Concomitant medications are defined as any medication given at least once between the day of first dose of study treatment and the last day of study visit, including those which were started pre-baseline and continued into the treatment period. The below summary tables will be reported:

- Prior medication/procedures

- Concomitant medications/procedures which started prior to first dose of study treatment
- Concomitant medications/procedures which started on/after first of study treatment

All prior and concomitant medications will be coded using the most recent version of the WHO drug dictionary. All concomitant medications (general and ocular) will be listed and summarized in alphabetic order according to Anatomical Therapeutic Chemical (ATC) classification system and PT. Tables will also show the overall number and percentage of patients receiving at least one treatment of a particular ATC.

For prior and concomitant ocular medications, as well as ocular procedures performed during the study, separate tabular summaries will be prepared for the study eye and the fellow eye. A listing of all prior and concomitant medications and concomitant procedures will be provided.

For AESIs, a separate summary of prior and post aVEGF therapies will be provided.

For handling of missing or incomplete start and end dates, see [Appendix 5.1.3](#) of this document.

All summaries will be performed on the Safety set.

2.5.3 Prior and concomitant Surgery and Procedures

All prior and concomitant surgery and procedures indications will be summarized and listed by category (general, ocular) and eye (study, fellow, any).

For handling of missing or incomplete start and end dates, see [Appendix 5.1.3](#) of this document.

All summaries will be performed on the Safety set.

2.5.4 History of anti – VEGF Therapy

The anti-VEGF therapy will be collected in CRF at Baseline. All recent anti-VEGF therapy will be listed and summarized. Table will present nature of the previous anti-VEGF, summary statistics for total number of previous IVTs, number of patients and percentages of previous anti-VEGF (3,4,5,6...), summary statistics for time since first anti-VGEF, time since last anti-VEGF along with below interval summary statistics.

1. Inclusion vs last anti-VEGF
2. Last anti-VEGF and second anti-VEGF
3. Second last anti-VEGF and third last anti-VEGF

The listing will include nature of the previous anti-VEGF, date of the last anti-VEGF treatment, interval of the last anti-VEGF treatment, date of the second last anti-VEGF treatment , interval of the second last anti-VEGF treatment, date of the third last anti-VEGF treatment, interval of the third last anti-VEGF treatment, date of the first anti-VEGF treatment, interval of the first anti-VEGF treatment and total number of anti-VEGF treatments (including the last one).

The below characteristics prior to first anti-VEGF will be summarized.

1. The summary statistics of BCVA and CSFT.
2. Number and percentage of IRF, SRF and Sub-RPE.
3. Summary statistics of height for IRF, SRF, Sub-RPE (if available).

The listing of above last anti-VEGF characteristics will include patients identification number, therapies name and date of therapy, BCVA, CSFT, IRF, SRF, Sub-RPE and height for IRF, SRF, Sub-RPE (if available). The above analysis will be performed on the Safety set.

2.6 Analysis of the primary objective

2.6.1 Primary endpoint

The primary objective of this study is to evaluate the effect of brolucizumab 6 mg on disease control. The primary efficacy endpoint is the proportion of patients with no disease activity at Week 16 in the study eye.

Estimation for the proportion of disease control involves only calculating the ratio of successes. In this study

Event: 1= no disease activity (disease control)

0= disease activity (failure)

Count: Frequency or number of patients with no disease activity (disease control) at Week 16.

Proportion: Number of patients with no disease activity (disease control) at Week 16/Total number of patients in the FAS.

The number of disease control patients at Week 16, total number of evaluable patients, percentage of disease control and 95% confidence interval (CI) using the Clopper-Pearson method will be provided.

Sensitivity analysis will be performed for primary endpoint using last observation carried forward (LOCF) method and considering disease activity for missing data at Week 16.

A sensitivity analysis in patients exposed and not-exposed to USM will be performed for below estimand.

- a) Proportion of patients with no disease activity at Week 16.
- b) Status of patients with disease activity before and after introduce of USM.

The above analysis will be done on the FAS and only on the study eye.

The analysis will be performed on the PPS, if there is more than a 10% difference in patients, between FAS and the PPS.

2.6.2 Supportive analyses

Subgroup analysis according to patient characteristics, like gender (male, female), age class (< 50, 50 - 65, 65 - 75, 75 - 85, \geq 85), Baseline fluids type (IRF, SRF, both), number of previous anti-VEGF injections (3, 4 - 6, 7 - 9 and \geq 10), interval (in week) since previous anti-VEGF injection (4, 5, 6, 7, 8) and time since nAMD diagnosis (2.5 - 5 month, 5 - 8 months, 8 - 11 months, 11 - 18 months and $>$ 18 months).

2.7 Analysis of secondary efficacy objective(s)

2.7.1 Secondary endpoints

2.7.1.1 Long term disease activity criteria

The first secondary objective of this study is to evaluate the effect of brolucizumab 6 mg on disease control at Week 48. The first secondary efficacy endpoint is the proportion of patients with no disease activity (disease control) at end of study (EOS) Week 48.

The number of disease control patients at Week 48, total number of evaluable patients, percentage of disease control and 95% confidence interval (CI) using the Clopper-Pearson method will be provided.

The above analysis will be done on the FAS and only on the study eye.

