A planned study visit schedule will be established at Screening/Baseline/Day 1 for all patients. All post-Screening/Baseline and/or subsequent scheduled visits will be calculated based on the Day 1 visit date. During the Treat-to-Control Phase, from Week 8 to Week 44/46, the treatment visit intervals will be determined by the Investigator, based on the patient's disease activity (see [Section 6.7.2](#)). All efforts should be made to adhere to all scheduled visits and assessments as outlined in the assessment schedule ([Table 8-1](#)).

A \pm 7-day visit window will be allowed should the patient be unable to return per the scheduled visit. All efforts should be made to revert back to the planned visit schedule taking into consideration the restrictions on the minimum treatment interval for the study medication (brolucizumab).

Assessments can be performed on 2 consecutive days in which both days must occur within the visit window.

Treatment is intended to be administered on the day of the study visit, or if this is not possible, within 3 days after the study visit at which the per-protocol assessments took place. If study visit assessments and the corresponding treatment occur on separate days, a repeat safety check-up should be performed prior to treatment of the eye and results documented in the source documents. For all visits, efficacy assessments ([Section 8.3](#)) and safety assessments ([Section 8.4](#)) should be performed prior to any administration of study treatment.

Missed or rescheduled visits should not lead to automatic discontinuation.

If the COVID-19 pandemic limits or prevents on-site study visits, study treatment could not be administered and other study assessments may not be performed. Alternative methods of safety monitoring may be implemented. Depending on local regulations, site capabilities and patient's visit status in the study, phone calls or virtual contacts (e.g. teleconsult) can be performed for safety follow-up for the duration of the pandemic, until it is safe for the participant to visit the site again.

Patients who prematurely discontinue study treatment for any reason should return for the EOS visit assessments as scheduled in [Table 8-1](#), except for patients who withdraw their consent from the study and do not wish to do so (refer to [Section 9.1.2](#)).

Table 8-1 Assessment schedule for the study eye

Period	Treatment Period					Follow-up	
	Initiation Phase			Treat-to-Control Phase			

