14) The week 48/50 EOS assessments only apply to patients who completed the study per protocol. The assessments are not required for subjects who have undergone ETD assessments and continued in the study without study treatment.

15) ETD: Early treatment discontinuation applies to subjects who discontinue early from study treatment and continue in the study. The assessments should be performed 4 weeks after the last injection of study drug. This can occur at any time point.

16) For patients who continue in the study after ETD and up to Week 48/50 (end of study) while patient is on standard of care. Additional safety assessments and imaging can also be performed if required, as per investigators discretion. In addition, after ETD, subjects are not required to attend the mandatory visits at Week 16 and Week 48/50. The last visit should be at week 48. This can occur at any time point.

Assessments in the fellow eye

The fellow eye will be examined (data collected and analyzed) only at the Screening/Baseline and the Week 48/EOS visits as follows:

- At Screening/Baseline: BCVA, ophthalmic examination, [REDACTED] OCT, [REDACTED].
- At Week 48/EOS: BCVA, ophthalmic examination, [REDACTED] OCT [REDACTED].

Other assessments of the fellow eye may be performed at the Investigator's discretion in accordance with routine practice at other time points; however, these will not be collected or analyzed in this study.

All data obtained from these assessments must be supported in the patient's source documentation.

Concerning Odysight® optimal self-assessment, only best-corrected near visual acuity (BCNVA) for the study eye will be analyzed. It is not requested for the purpose of this study to do any self-assessment measure of the fellow eye.

Unscheduled visits

For patients who return to the study site before the next scheduled study visit, the Investigator will capture the unscheduled visit in the eCRF only in the case of a clinically significant abnormality finding.

If this finding leads to an AE and/or the decision to treat the patient prior to the next scheduled treatment, all the procedures listed for the interim visit need to be conducted and captured in the eCRF.

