9.1 Discontinuation

9.1.1 Discontinuation of study treatment

Discontinuation of study treatment for a patient occurs when study treatment is stopped earlier than the protocol planned duration and can be initiated by either the patient or the Investigator.

The Investigator must discontinue study treatment for a given patient if he/she believes that continuation would negatively affect the patient's well-being.

The Investigator and/or referring physician will recommend the appropriate follow-up medical care, if needed, for all patients who are prematurely withdrawn from the study.

Study treatment must be discontinued under the following circumstances:

- Patient requires treatment on a q4w interval after the initiation phase (Week 14/Week16), i.e., after the three-monthly injections at Baseline, Week 4, and Week 8, followed by the first interval extension

- Patient develops intraocular inflammation, including retinal vasculitis and/or retinal vascular occlusion
- Patient/guardian decision
- Pregnancy
- Use of prohibited treatment
- Any situation in which study participation might result in a safety risk to the patient

If premature discontinuation of study treatment occurs, the following should be done as appropriate:

- The Investigator should make a reasonable effort to understand and document the primary reason for the patient's premature discontinuation of study treatment using the appropriate eCRF page.
- Patients who prematurely discontinue study treatment for any reason should return 4 weeks after last study treatment to perform the assessments for early treatment discontinuation (ETD). Please refer to [Table 8-1](#), except for patients who withdraw their consent from the study and do not wish to do so (refer to [Section 9.1.2](#)).
- After these assessments are performed, patient can be switched to standard of care (SOC) anti-VEGF IVT as per investigators discretion. IVT injection is contraindicated in patients with active intraocular or periocular infections and in patients with active intraocular inflammation; therefore, the investigators must verify that these conditions are not present in the study eye prior to every injection.
- After premature study treatment discontinuation, at a minimum till week 48, in abbreviated visits, the following data should be collected at clinic visits or via telephone/email contact:
 - New/concomitant treatments
 - Adverse events/Serious Adverse Events
 - BCVA

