12.8 Sample size calculation

The sample size calculation is based on the hypothesis of 25% to 35% of patients with no disease activity at Week 16. The sample size analyses were performed before the urgent safety measures were introduced.

Table 12-1 Confidence intervals for proportions (2 sided)

Confidence level	Sample size (N)	Expected proportion	Target distance from proportion to limit
0.950	250	0.25	0.054
0.950	300	0.25	0.049
0.950	325	0.25	0.047
0.950	400	0.25	0.042
0.950	250	0.30	0.057
0.950	265	0.30	0.055
0.950	300	0.30	0.052
0.950	325	0.30	0.050
0.950	400	0.30	0.045
0.950	250	0.35	0.059
0.950	300	0.35	0.054
0.950	325	0.35	0.052
0.950	400	0.35	0.047

A sample size of 250 to 400 patients produces a 2-sided 95% confidence interval with a distance from the proportion to the limits ranges from 0.042 to 0.059 when the estimated proportion varies from 0.25 to 0.35 (nQuery Advisor version 7.0).

In the HAWK and HARRIER studies, the proportion of naïve nAMD patients treated with brolucizumab who had disease activity at Week 16 was 30% less than for patients treated by aflibercept.

To determine a similar 30% proportion of patients with no disease activity at Week 16 in this pretreated study with a precision of 5.5% and alpha 5% (2-sided 95% confidence interval of width 11%), a total of 265 patients have to be observed in this study.

Considering a dropout rate of 10%, a total of 295 patients will be included.

13 Ethical considerations and administrative procedures

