Percent change from Baseline: The percent change from baseline will be calculated as below: $((\text{post-baseline value} - \text{Baseline value}) / \text{Baseline value}) * 100$.

Proportion: A proportion refers to the fraction of the total that possesses a certain attribute. In this study attribute is disease free activity.

Disease control: When patients have no disease activity after taking study treatment then patient will be consider as disease control.

On-treatment period: The on-treatment period lasts from the date of first administration of study treatment to 30 days after the date of the last actual administration of any study treatment.

Treatment duration: The maximum planned duration of treatment for each patient is 44 to 46 weeks in accordance with the designated treatment regimen. Discontinuation of study treatment for a patient occurs when study treatment is stopped earlier than the protocol planned duration and can be initiated by either the patient or the investigator.

Treatment discontinuation: When patients discontinue study treatment but continue in the study, the efficacy data will be used at the time the patient stopped study treatment.

Last interval: The last treatment interval (defined by the investigator) before Week 48.

Maximum interval: The longest interval of treatment reached by the patient over the study period.

Event for no disease activity: When patients will be with no disease status as per investigator decision after last dose in initiation phase then the patients will consider as event for no disease activity. If patients with active disease status or early discontinue then patients will be considered as censored for disease activity.

Dry retina: Absence of fluid (IRF/SRF/ sub-RPE) will be considered as dry retina.

Event for dry retina: When patients have absence of fluid then it will be considered as an event of dry retina. If patients have a presence of fluid before/at EOS or early discontinuation then will be censored.

[figure not shown]
Study eye and fellow eye: The investigator selects the eye with the worse BCVA at Screening as the study eye if both eyes are eligible as per the inclusion and exclusion criteria, unless the investigator deems as a study eye more appropriate to select the eye with better BCVA, based on medical reasons or local ethical requirements. If both eyes are eligible as per the inclusion and exclusion criteria, then it is recommended to select the right eye as the study eye.

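### The Week 48 disease-control percentage has no stated denominator or missing-data rule, although patients stopped for q4w need or inflammation have no Week 48 reading scheduled or required

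*SAP*

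**What the plan says.** Table 2-1 of the protocol and SAP 1.2 give long-term disease control a single endpoint: the proportion without disease activity at Week 48. SAP 2.7.1.1 reports "The number of disease control patients at Week 48, total number of evaluable patients, percentage of disease control" with a Clopper-Pearson interval, in the study eye and on the FAS. Protocol 12.5.1 adds no denominator.

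The Week 16 text is fuller. SAP 2.6.1 uses the same evaluable phrase but also writes the ratio: "Proportion: Number of patients with no disease activity (disease control) at Week 16/Total number of patients in the FAS". It adds two sensitivity analyses, one by LOCF and one counting missing readings as active disease.

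Protocol 9.1.1 lists mandatory reasons to stop study treatment. One is "Patient requires treatment on a q4w interval after the initiation phase (Week 14/Week16"); another is IOI, including retinal vasculitis (RV) and/or retinal vascular occlusion (RO). Stopped patients have an ETD visit four weeks after the last injection. After that, the follow-up column of Table 8-1 carries only medications, adverse events and BCVA. Footnote 14 says of the Week 48/50 assessments: "The assessments are not required for subjects who have undergone ETD assessments and continued in the study without study treatment". Footnote 16 and the later text of 9.1.1 agree. Yet the text of Protocol Section 8 just before the table says: "Patients who prematurely discontinue study treatment for any reason should return for the EOS visit assessments as scheduled".

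On data after a stop, Protocol 12.4.3 (in the primary-endpoint section) censors efficacy data from that time. SAP 2.1.1 instead says the efficacy data at the time of stopping are used.

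**The concern.** Whether a patient has a Week 48 reading depends partly on the outcome. A patient judged to need q4w dosing is taken off study treatment, and the reading that would record the lack of control is then no longer required. If the percentage is taken over patients with a Week 48 reading, these patients leave both numerator and denominator. The result then describes mainly patients still on drug. It would also sit beside a Week 16 percentage whose written denominator is the whole FAS, so control could seem to improve between the two visits merely because failures had dropped out.

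A likely source of the gap is that SAP 1.1 still describes a regimen in which patients with activity may be kept on or returned to four-week intervals and followed to Week 48/50. The current protocol stops them. The two descriptions need reconciling, and the Week 48 analysis text has no rule for the group that is now stopped.

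**Working it through.** **1. The plan's own figure.** Protocol 12.8 concerns Week 16 only: "The sample size calculation is based on the hypothesis of 25% to 35% of patients with no disease activity at Week 16", and, at 30%, "with a precision of 5.5% and alpha 5% (2-sided 95% confidence interval of width 11%), a total of 265 patients". With n = z²p(1−p)/d², z = 1.96, p = 0.30 and d = 0.055, n = 266.7, so 267 against the stated 265. The half-width at 265 is 0.0552. Inflating, 265/0.90 = 294.4, so 295 as stated. The figure reproduces, but it gives no Week 48 control or stop rate.

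**2. Is an ETD reading a Week 48 reading?** The SAP 2.2 window for Week 48 is Day 330–342. A visit exactly 28 days after the last injection falls there only if that injection was on Day 302–314, which is the SAP's Week 44 window. A patient stopped after a Week 14 or Week 16 injection has the ETD reading around Week 18 or 20. That reading is taken four weeks after an injection. If carried forward, it could classify a patient stopped for needing q4w dosing as controlled at Week 48.

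**3. Effect of the denominator.** Let s be the share of the FAS stopped and without a Week 48 reading, and c the control rate among those read. The evaluable result is c. The FAS result, with stopped patients counted as not controlled, is c(1−s). The gap is c − c(1−s) = c × s. Both c and s are assumptions.

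At c = 60%:
- s = 10%: 60% against 54%, gap 6 points.
- s = 30%: 60% against 42%, gap 18 points.

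At c = 70% with an FAS of 295, whole patients and Clopper-Pearson intervals:

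| Stopped | Read | Controlled | Evaluable % (95% CI) | FAS % (95% CI) | Gap |
|---|---|---|---|---|---|
| 10% | 266 | 186 | 69.9 (64.0–75.4) | 63.1 (57.3–68.6) | about 7 |
| 30% | 206 | 144 | 69.9 (63.1–76.1) | 48.8 (43.0–54.7) | about 21 |
| 50% | 148 | 104 | 70.3 (62.2–77.5) | 35.3 (29.8–41.0) | about 35 |

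For scale, the gap at 10% stopped already exceeds the 5.5-point precision sought at Week 16.

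**The case against.** A reader might infer that the SAP divides by evaluable patients and that an upward bias is therefore built in. The documents do not say so. SAP 2.7.1.1 lists the evaluable count, writes no ratio and places the analysis on the FAS. In SAP 2.6.1 the same phrase stands beside an explicit FAS denominator. The evaluable reading is permitted, not stated.

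Other strong readings also fail:
- *No Week 48 reading can exist.* The footnotes say not required, and Section 8 can be read as asking discontinuers to return. A late ETD visit could also fall in the window.
- *Only successes remain.* Under Protocol 6.7.2.2, activity at a 10- or 14-week inspection visit leads to a shorter interval, not a stop. Such patients can be on drug and active at Week 48.
- *The SAP censors discontinuers out of this proportion.* SAP 2.1.1 says: "If patients with active disease status or early discontinue then patients will be considered as censored for disease activity". Applied to a proportion, that would remove every active patient and give 100%. It reads as time-to-event coding, parallel to the dry-retina definition that follows and the Kaplan-Meier analysis in SAP 2.7.1.2.4.
- *The 65–75% expected to be active at Week 16 will be stopped.* The current text states an automatic stop on activity only at the Week 14 inspection visit. Otherwise the criterion is an investigator's judgement that q4w dosing is required.

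The best defence is that the ETD reading stands in for the end-of-study reading: SAP 2.1.1 can be read that way, and Protocol 9.1.1 says the assessments need not be repeated because they were done at ETD. That would give stopped patients a value, but it conflicts with Protocol 12.4.3 and has the carry-forward problem shown above. It is also fair that the endpoint is descriptive, that stop reasons are tabulated, and that a reader with the controlled count and the FAS size can compute the FAS percentage. That does not settle whether ETD readings are in the count.

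**Conclusion.** The point holds as an unresolved specification with a foreseeable direction of error, not as an established bias. Analysts following the SAP could defend an FAS denominator, an evaluable denominator, or ETD readings used as Week 48 results, and these can give materially different figures. The evaluable version would overstate long-term control relative to the FAS with stopped patients counted as not controlled: by about 6–7 points if 10% are stopped and about 18–21 points if 30% are, assuming 60–70% control among those read. The documents give no Week 48 control or stop rate; the 10% planned dropout belongs to the sample-size calculation and is not a forecast of treatment stops.

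The change should be made because this is the only endpoint for the first secondary objective. The written Week 16 denominator and the sample size are not affected.

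**What to change.** In SAP 2.7.1.1:
- Write the proportion as patients with no disease activity at Week 48/50 divided by all FAS patients, matching Week 16.
- Count as not controlled those stopped for q4w need, lack of efficacy or use of another anti-VEGF in the study eye, and those with no Week 48 reading. Do not carry an ETD reading forward as Week 48 control.
- Show IOI, RV and RO stops on a separate line, with a sensitivity analysis of how they are counted. Inflammation is not nAMD activity, so treating it as failure is an estimand choice that should be visible.
- Give the evaluable-patient percentage as supplementary, with evaluable defined and the numbers stopped by reason.

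In SAP 2.1.1, state that the censoring definition applies only to time-to-event displays. Reconcile the Section 8 instruction on returning for end-of-study assessments with Table 8-1 footnotes 14 and 16 and Protocol 9.1.1, and Protocol 12.4.3 with the SAP 2.1.1 rule on data at treatment stop.

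The cost is SAP wording and a few table lines. No new data are needed: stop reasons are already summarised under SAP 2.4.1, and the urgent safety measure set in SAP 2.3 identifies patients needing q4w dosing. The downside for the sponsor is a lower reported Week 48 figure than the evaluable version would give.
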